3.0 Objectives

AIM 1A: Determine whether and to what degree balance is altered in CSM. The degree of COP sway will be compared between CSM and controls in the six conditions comprising VETS testing.

Hypothesis 1: Impaired proprioceptive transmission in CSM will result in poorer balance (larger COP sway area) during EC conditions (eliminating the ability to compensate with visual feedback) and FOAM (reducing the reliability of somatosensory feedback) conditions compared to healthy veterans.

AIM 1B: Determine whether VETS enhances sensitivity and selectivity in the diagnosis of CSM. Composite measures of balance will be related to clinical assessment tools and their relationship with MRI.

Hypothesis 2: VETS will provide additional sensitivity and selectivity in identifying CSM compared to current clinical assessment tools.

Hypothesis 3: The degree of COP sway area during EC and FOAM conditions is expected to directly relate to the degree of spinal cord compression quantified from MRI, leading to a more sensitive gradation in the severity of CSM.

AIM 2: Evaluate the VETS scores after surgery for CSM. The degree of COP sway area under the 6 conditions will be compared before surgery, 2 weeks, 6 weeks, and 6 months after surgery.

Hypothesis 4: We expect surgery to reduce COP sway in EC conditions

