5.0 Study Procedures

5.1 Study Design

For AIM 1, a cross-sectional design that includes within-subjects (VETS conditions) and between-subjects (veteran groups) factors will be used to compare balance and posture in patients awaiting surgery for CSM ($n = 20$) to a cohort of age and gender-matched non-CSM controls ($n = 20$). The 20 veterans with CSM recruited for AIM 1 will also serve as the sample for AIM 2, which is a longitudinal assessment of balance following surgical intervention for CSM. The data generated from the proposed study will provide a base estimate of the variance in our veteran groups for use in the power calculation for a larger follow up study

Veteran volunteers (CSM and control) meeting eligibility criteria will complete one session of VETS balance testing. Those veterans awaiting surgery for CSM will be asked to return for three additional sessions of VETS at designated time points scheduled 2 weeks, 6 weeks, and 6 months post-surgery. For returning CSM veterans, self-report measures will be collected at each additional time point to compare objective (VETS) and subjective (scale measures) assessments of functional impairment related to CSM following surgery. None of the procedures involved in this research project will alter standard of care associated with CSM or the surgical treatment. “Each patient will be cleared by one of the study doctors ([name], [name], or [name]) before participating in the post-surgery sessions. In the event that a patient is found to be physically incapable of safely participating in the first post-surgery session, they will not continue participation in the study until they are cleared by the study doctors. Thus, even if a patient is not cleared to participate in the two week post-surgery time point, they may be cleared to participate in the remaining two sessions (six weeks and six months post-surgery).”

Risks/Benefits of Participation

There are no risks associated with the questionnaires included in this study, as they ask only about physical symptoms and functioning associated with CSM. Although some emotional health questions will be included, they are not expected to be upsetting in any capacity.

The risks associated with VETS testing are minimal and are as follows:

- Discomfort from standing on the WBB or foam for a prolonged period of time
- Dizziness or disorientation when viewing the dynamic condition

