All statistical analyses will be performed using IBM SPSS Statistics Version 24 and MedCalc. For descriptive purposes, continuous data will be summarized with the number of non-missing values, mean, and standard deviation, minimum, median, and maximum and categorical data will be summarized with the number of non-missing values and the numbers (frequencies) of values equal to each of the possible categories, unless stated otherwise. Univariate analyses will examine data distributions, potential outliers and missing data. All statistical tests will be two-sided with a significance level of alpha=0.05. Unless otherwise stated, no multiplicity adjustment will be applied and no missing values will be imputed. For analysis of posturography data, each of the six VETS postural conditions (see Figure 2) will be tested three times for each participant from which an average is calculated for each condition. These within-subject, within-condition averages will be used in model building to assess between groups differences in balance (AIM 1a) and within-groups change in balance over time following surgical intervention (AIM 2).

For **AIM 1a**, mixed model ANOVA will be used to compare veteran group (CSM vs Control) and within-subject visual (EO, EC, and DYN) and surface conditions (FIRM and FOAM). Average COP sway, COP velocity, and MSE of COP sway velocity for each of the six VETS conditions will serve as dependent measures in separate models. Using Mauchly's tests, violations of sphericity will be detected, are corrected with Greenhouse-Geisser adjustments.

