For **AIM 1b**, receiver operating characteristic (ROC) analyses will be conducted as a preliminary determination of sensitivity and specificity of VETS conditions to detect CSM. We will assess areas under the curve (AUC) and corresponding 95% confidence intervals, which will serve as indices of accuracy for CSM diagnosis. Using known groups (CSM and control veteran volunteers), we will compare AUC curves corresponding to 1) traditional diagnostic scale measures (e.g., mJOA scale, Nurick Scale, NDI, and SF-36), 2) VETS conditions, and 3) scale measures combined with VETS conditions. These analyses will serve as indicators for the degree the posturography, alone or in combination with scale measures, are sensitive and selective to CSM. An AUC = 0.50 will be considered chance level for correct classification into CSM and control groups. Differences in AUC for each of the three ROC curves will be accomplished using methods described by Delong et al ⁴⁵.

For **AIM 2**, VETS data for CSM veterans will be assessed for changes in balance following surgical intervention. VETS dependent measures outlined above will be entered into repeated-measures ANOVA with time point (pre-surgery, 2 weeks, 6 weeks, and 6 months post-surgery) entered as an additional repeated measure. Using Mauchly's tests, violations of sphericity will be detected, are corrected with Greenhouse-Geisser adjustments.

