5.7 Withdrawal of Subjects

Subjects will be told that they may withdraw from the study at any time. As soon as the subject notifies the PI or researcher that they wish to cease their participation in the study, any appointments will be canceled and the participant will be paid for any sessions partially or fully completed.

Participants may be withdrawn without their consent if the study is suspended during their participation or they suffer a health-related event within the time frame of their participation that precludes them from participating further, including complications from surgery.

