6.0 Reporting

Adverse Event (AE): If a research participant exhibits acute discomfort as noted by the researcher during a testing session (e.g., expressing discomfort or overwhelming disorientation while standing on the VETS apparatus), they will be asked if they feel they are able to carry on with the session and offered a break. If they are unable to carry on, the PI will be informed immediately and the testing session will be terminated for the day.

Serious Adverse Event (SAE): An example of a SAE would be a participant suffering severe complications associated with the CSM surgical treatment. It is likely that such complications will occur only unrelatedly to any study activities—especially if a participant is prohibited from active participation while experiencing such complications. In the event that a participant has a strongly negative response to the surgery, the participant will not be scheduled for any post-surgical appointments.

An AE temporally related to participation in the study will be documented whether or not considered related to the test article or procedure. This definition includes current illnesses and injuries and exacerbations of preexisting conditions including changes to psychological state. AE will be kept in the subject tracking log and reported as a summary at continuing review. Expected adverse events which are not serious are reported on the Continuing Review Progress Report (CR). Any unanticipated adverse event related to application of tDCS will be reported to the IRB within 10 days, as per Federal Regulations Title 21 812.150 (1).

SAE, such as hospitalization for more than 24 hours, will be reported to the IRB within 5 days per SOP 151-17. This will be accomplished by submitting an adverse event report to the IRB.

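### AIM 2's repeated-measures ANOVA drops any patient who misses one session, including those the protocol brings back, and no analysis addresses patients left untested because of surgical outcome

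*Combined protocol and SAP*

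**What the plan says.** Section 3.0 sets the AIM 2 comparison: "The degree of COP sway area under the 6 conditions will be compared before surgery, 2 weeks, 6 weeks, and 6 months after surgery". Under Hypothesis 4, sway is expected to fall after surgery in the eyes-closed (EC) conditions, and no visit is named.

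Section 5.6 gives the method: "VETS dependent measures outlined above will be entered into repeated-measures ANOVA with time point (pre-surgery, 2 weeks, 6 weeks, and 6 months post-surgery". Time is added to the visual and surface factors, with Mauchly's test and the Greenhouse-Geisser correction. The general rules in the same section say "no multiplicity adjustment will be applied and no missing values will be imputed". Their other provisions on missing data are descriptive: "Univariate analyses will examine data distributions, potential outliers and missing data", and continuous summaries are to include the number of non-missing values.

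Three places govern who is tested after surgery:
- Section 5.1, on patients not fit for the first post-surgery session: "they will not continue participation in the study until they are cleared by the study doctors". It then allows that "they may be cleared to participate in the remaining two sessions (six weeks and six months post-surgery".
- Section 5.7 permits withdrawal without consent if "they suffer a health-related event within the time frame of their participation that precludes them from participating further, including complications from surgery".
- Section 6.0: "In the event that a participant has a strongly negative response to the surgery, the participant will not be scheduled for any post-surgical appointments".

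**The concern.** There are two points, with different causes and different remedies.

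**Discarded data.** The protocol foresees a missed 2-week session and makes room for the patient to return. The named analysis cannot use a patient with an incomplete record, so the later sessions are collected and then left out. The plan never uses the term complete-case; the deletion follows from the method together with the ban on imputation.

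**Selective non-testing.** This comes from the testing rules and would exist under any model. Patients who do badly after surgery may have no post-surgery sway measurement, and the AIM 2 result would then describe mainly those who did well enough to be tested. No planned analysis would show whether the result depends on that.

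**Working it through.** **Inputs from the documents.** 20 CSM patients (sections 5.1 and 5.2); 4 time points, 3 visual conditions and 2 surfaces (section 5.6). There is no missed-visit rate, SD, between-visit correlation or power figure, so there is no stated result to reproduce. Every rate and correlation below is an assumption.

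**Cells lost per returning patient.** A complete record has 4 × 3 × 2 = 24 cells. A patient who misses only the 2-week session supplies 3 × 6 = 18, and all 18 are dropped. If 4 of 20 do this, 80 − 4 = 76 sessions are observed and 4 × 3 = 12 of them are discarded.

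**Precision, pre-surgery to 6 weeks or 6 months.** If k patients miss only the 2-week session, all 20 still have both ends of these contrasts. The standard-error ratio, complete-case over all-available, is √(20/(20 − k)):
- k = 2: √(20/18) = 1.054
- k = 4: √(20/16) = 1.118
- k = 6: √(20/14) = 1.195

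**Precision, pre-surgery to 2 weeks.** Assume compound symmetry with unit variance and correlation ρ. Let v = 2(1 − ρ) be the variance of a change, and e = 1 − 3ρ²/(1 + 2ρ) the variance of the 2-week value given the other three. The squared ratio is [v/(20 − k)] ÷ [e/(20 − k) + (v − e)/20].
- ρ = 0.3: v = 1.4, e = 0.831; ratios 1.021, 1.043 and 1.067 for k = 2, 4 and 6.
- ρ = 0.8: v = 0.4, e = 0.262; ratios 1.018, 1.037 and 1.056.

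**Selection on surgical outcome.** Suppose there is no true change, individual changes are standard normal (negative means improvement), and the k patients with the worst response score are never tested. The score has correlation r with sway change. The expected shift in the observed mean is −r × (sum of the k largest expected normal order statistics for 20) ÷ (20 − k). The two largest are about 1.867 and 1.408.
- k = 1: r = 0.3 gives 0.3 × 1.867/19 = 0.03 SD; r = 0.8 gives 0.08 SD.
- k = 2: r = 0.3 gives 0.3 × 3.275/18 = 0.05 SD; r = 0.8 gives 0.15 SD.

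In simulation, false claims of improvement (nominal 2.5%) were 3% to 6% with one patient lost and 4% to 11% with two. With nobody lost there is no bias.

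**What a likelihood model removes.** If lost patients have only a baseline, the share of bias left is approximately (1 + ρ)/2 under compound symmetry: 65% at ρ = 0.3 and 90% at ρ = 0.8. Simulation gave 65% to 67% and 90%.

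**What a two-part sensitivity analysis shows.** With no true change and r from 0.3 to 0.8, assigning lost patients no change leaves −0.03 to −0.13 SD, and assigning the worst observed change gives +0.01 to +0.12 SD. The pair does not always contain the truth. At r = 0.9 and 1.0 the worst-observed result is itself negative (about −0.01 to −0.05). With a true change of −0.60 SD, r = 0.3 and two lost, the pair is −0.589 and −0.475, and both miss −0.60.

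**The case against.** The strongest reply is that this is a pilot. Section 5.2 sets the sample size on feasibility, section 5.1 says the data will supply variance estimates for a larger study, and no power is claimed. That stands, and it limits the importance of the precision loss. The pre-surgery group variances are not affected. A reader might infer that AIM 2 is seriously compromised; without a missed-visit rate the documents do not support that.

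A reader might also infer that sections 5.1, 5.7 and 6.0 contradict one another. They can be read as tiers: pause until cleared, withdraw for a precluding event, and no sessions after a severe reaction. What is missing is the boundary between a paused patient and one never tested again. That calls for clarification; it is not a proven contradiction.

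Nor does the plan ignore missing data. It will examine them, count non-missing values and log adverse events. Applied by visit, the counts would show how many were tested. They would not show why others were not, or whether the result depends on them.

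Finally, section 5.6 uses the term mixed model ANOVA, but only for AIM 1a, where it means between- and within-subject factors with the same sphericity tests. It does not retain incomplete records in AIM 2.

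**Conclusion.** The first point holds on the text alone: the planned AIM 2 model would drop patients whom section 5.1 expressly allows back. Its size is modest and rests on assumed numbers of missed sessions: standard errors 5% to 20% larger for the two later contrasts and 2% to 7% larger for the 2-week contrast, with 2 to 6 of 20 patients affected.

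The second point holds conditionally. The rules let testing depend on surgical outcome, and no analysis addresses this. It is tempting to conclude that AIM 2 is biased in favour of surgery. That needs a link between poor response and larger sway, and actual losses, neither of which the documents establish. Given both, the tilt toward Hypothesis 4 is about 0.03 to 0.08 SD for one patient lost and 0.05 to 0.15 SD for two, at correlations of 0.3 to 0.8. A mixed model would remove only part of it.

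Both should be fixed before analysis. Neither invalidates the study.

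**What to change.** **Model.** Analyse AIM 2 with a likelihood-based linear mixed model (MIXED in the planned SPSS) that uses every attended session. Keep time, visual and surface factors so that all six conditions are still compared, and report the EC contrasts of pre-surgery with each post-surgery visit. Prespecify a covariance that 20 patients can support. It should not be a random intercept alone: with assumed variance shares of 0.50 participant, 0.15 participant-by-time and 0.35 residual, that gives a type I error near 10% for the EC contrast. Let variances differ by condition, because section 2.0 reports larger sway with eyes closed on foam and its spread may differ too. Where estimable, let visit-to-visit change differ by visual condition, because Hypothesis 4 is specific to EC. Name a small-sample degrees-of-freedom method such as Satterthwaite.

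**Untested patients.** Reconcile sections 5.1, 5.7 and 6.0 so that it is clear who is invited to each session; no rule is proposed here. Report the number not tested at each visit, by reason. Add a sensitivity analysis that assigns patients untested because of surgical outcome no improvement, then the worst observed change. Present it as a check on robustness, not as bounds that contain the true effect.

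**Cost.** SAP wording, clarified protocol text and slightly more analysis; no extra patients or visits. At n = 20 the degrees of freedom are approximate and the covariance may still be misspecified. The worst-change analysis is deliberately pessimistic.

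### The AIM 2 ANOVA F tests have no direction and do not isolate the eyes-closed conditions, so section 5.6 contains no test of Hypothesis 4

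*Combined protocol and SAP*

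**What the plan says.** Section 3.0 states the prediction: "Hypothesis 4: We expect surgery to reduce COP sway in EC conditions". It has a direction (a reduction) and a location (EC, on both surfaces), but no visit. The aim above it is broader: "The degree of COP sway area under the 6 conditions will be compared before surgery, 2 weeks, 6 weeks, and 6 months after surgery".

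Section 5.6 gives the AIM 2 analysis. The target is worded without direction: "VETS data for CSM veterans will be assessed for changes in balance following surgical intervention". The measures are "entered into repeated-measures ANOVA with time point (pre-surgery, 2 weeks, 6 weeks, and 6 months post-surgery) entered as an additional repeated measure". Because time is an additional factor, I read the model as time (4) x visual condition (3) x surface (2). The only further step is "Using Mauchly's tests, violations of sphericity will be detected, are corrected with Greenhouse-Geisser adjustments".

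The general rules in 5.6 add "All statistical tests will be two-sided with a significance level of alpha=0.05", and state that by default there is no adjustment for multiplicity. COP sway area is the primary measure. The sample is the 20 CSM veterans, a number set by feasibility. Nowhere does 5.6 name, for AIM 2, a planned contrast, a comparison with pre-surgery, a test within EC, a primary visit or a follow-up procedure after the F tests.

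**The concern.** A test of Hypothesis 4 has to answer whether EC sway is lower after surgery than before. None of the planned F tests asks that. The time effect asks whether the mean over all six conditions differs between any of the four visits. Time x visual (3 x 2 = 6 numerator df before correction) asks whether the visit pattern differs between any of the three visual conditions. A significant result from either is compatible with improvement, with worsening, or with a change outside EC.

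Any statement about EC would therefore rest on comparisons chosen after the data are seen. For sway area alone there are 2 surfaces x 3 post-surgery visits = 6 EC comparisons with pre-surgery. Unadjusted, the chance that at least one shows a significant reduction when nothing has changed is bounded by 6 x 0.025 = 0.15, against 0.025 for one planned contrast.

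A temporary early disturbance is a realistic pattern here: section 5.1 foresees that some patients may not be cleared for testing at 2 weeks.

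**Working it through.** The plan gives no SD, correlation, effect size or power for AIM 2, so there is no figure of its own to reproduce. Steps 1 and 2 are algebra; steps 3 and 4 rest on assumed values.

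**1. Direction.** Write the effect as k orthonormal within-patient contrasts with mean vector m and covariance S. Then F = n(m'm)/trace(S), and the Greenhouse-Geisser factor depends on S alone. Reversing the sign of every observation turns m into -m and leaves S unchanged, so F, its degrees of freedom and p are identical. One simulated data set gave p = 0.00083 both ways.

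**2. Location and visit.** Let a shift of size d occur in one visual condition. Centre the visit pattern and sum the squares.
- 2-week rise only, (0, d, 0, 0): (3/4)² + 3(1/4)² = 0.75, times d².
- Sustained fall, (0, -d, -d, -d): centred values 3/4, -1/4, -1/4, -1/4, again 0.75 d².

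Centring over visual conditions gives (2/3)² + 2(1/3)² = 2/3, whether the shifted condition is EC or DYN. The time x visual signal is 0.75 x 2/3 x d² = 0.5 d² in every case. With errors exchangeable over visits and visual conditions, the test has the same power for an EC benefit, a temporary EC worsening and a DYN-only change. In the time effect, an EC-only shift is diluted to d/3.

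**3. Size under one set of assumptions.** Assumed log-scale SDs: subject 0.5, subject-by-condition 0.25, subject-by-visit 0.2, residual 0.2. Also n = 20, d = 0.25, two-sided 0.05 and Greenhouse-Geisser tests. The last column counts the pre-surgery to 6-month EC contrast only when it is significant and negative.

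| True pattern | Time effect | Time x visual | EC contrast shows reduction |
|---|---|---|---|
| EC falls and stays down | about 17% | about 99% | 86 to 87% |
| EC up at 2 weeks only | not the relevant test | about 99% | about 2.5% |
| DYN up at 2 weeks only | not the relevant test | about 99% | about 2.5% |
| All conditions up at 2 weeks only | about 96% | not the relevant test | about 2.5% |

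Hand check of the contrast. The variance of the EC change, averaged over two surfaces, is 2 x (0.2² + 0.2²/2) = 0.12, so the SD is 0.346 and the SE is 0.346/√20 = 0.077. Then 0.25/0.077 = 3.2 standard errors, consistent with power of 86 to 87%. The 2.5% is simply one tail of a two-sided 0.05 test whose true value is zero.

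**4. Other assumptions.** With subject-by-visit SD 0.4 and residual SD 0.3, time x visual is significant for a temporary EC rise in 71 to 73% of trials. With residual SD 0.4 it is about 40%. The time effect for a temporary rise in all conditions is about 40% in both settings. The contrast also weakens: at 0.4 and 0.3 its SD is √(2 x (0.16 + 0.045)) = 0.640 and its SE 0.143, so 0.25 is only 1.7 standard errors.

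A separate check used a single condition over four visits, in SD units, n = 20:

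| Correlation between visits | F test, +0.5 SD at 2 weeks only | F test, sustained -0.5 SD | Contrast, sustained -0.5 SD |
|---|---|---|---|
| 0.5 | 56% | 56% | 57% |
| 0.7 | 80% | 81% | 78% |
| 0.8 | 94% | 95% | 92% |

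The first two result columns agree, as step 2 says they must. The F test cannot tell these situations apart.

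**The case against.** A reader might infer that the plan would miss a real EC improvement, because the time effect has only about 17% power for one. The documents do not support that. Visual condition is a factor in the planned model, so time x visual is a planned test, and under the same assumptions it has about 99% power, more than the EC contrast. At n = 14 it still has about 90%, against roughly 70% for the contrast. No loss of power can be claimed.

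A reader might also infer that a significant F will be announced as benefit. Nothing in the documents says so, and there is no success rule. Section 5.6 promises descriptive summaries, in which a temporary 2-week rise would be visible. In the Introduction the team followed significant interactions in its pilot data with comparisons between conditions and reported their direction. That makes a crude misreading less likely. It does not supply the missing test, because no such comparison is carried into 5.6.

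Nor do the documents make 6 months the decisive visit. Hypothesis 4 names none, and an improvement at 2 or 6 weeks would also fit it. The absence of a named visit is part of the gap.

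Two further points stand. The percentages depend on SDs and effects that the documents do not give. And this is a feasibility-sized pilot, open about two-sided, unadjusted testing, which lowers the stakes.

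**Conclusion.** The point holds as one of interpretation and direction. As written, section 5.6 contains no test of Hypothesis 4: the F tests ignore sign and do not single out EC or a visit. That conclusion is algebraic and needs no assumed values. The statement that time x visual responds equally to an EC fall, an EC rise or a DYN-only change assumes exchangeable errors.

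The size does depend on assumptions. A temporary 2-week EC worsening makes time x visual significant in about 99% of trials under the SDs in step 3, and in about 40 to 75% under the larger ones, while a 6-month EC contrast shows a false reduction in about 2.5% throughout. The log scale is only a device of the simulation; the point does not depend on it.

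Pilot status does not remove the issue. The study is meant to show how far surgery changes VETS scores and to inform a larger study. An estimated EC change with its interval serves that purpose; an F statistic does not. The change should be made, though the study is not compromised without it.

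**What to change.** In section 5.6, under AIM 2, pre-specify one contrast for Hypothesis 4: the change in COP sway area, averaged over EC-firm and EC-foam, from pre-surgery to one named post-surgery visit, with estimate, 95% CI and two-sided p value. Six months is a reasonable choice of visit, but the investigators should make it before looking at outcome data. Add one supporting contrast at the same visit, EC change minus EO change, to show whether the effect is specific to EC. Keep the omnibus F tests as secondary, and label any other visit or condition comparison exploratory.

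The cost is a few sentences, with no new data, visits or patients. The small downside is that the other two post-surgery visits become secondary for Hypothesis 4.
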